- Imminent preterm delivery due to maternal disease or fetal conditions
- Is not willing to wear CGM

Demographic information collected:

- Maternal age at enrollment (years)
- Gestational age at diagnosis of GDM (weeks)
- Gestational age at study inclusion (weeks)
- Gravidity and parity (G_P_ _ _ _)
- Race or ethnic group (self reported, Black, White, Asian, Hispanic, Other)
- Smoking status (current use in pregnancy at time of enrollment, yes/no)
- Alcohol use (current use in pregnancy at time of enrollment, yes/no)
- BMI at study entry (weight in kg / height in m²)
- History of GDM in a prior pregnancy (yes/no)
- Result of 50g OGTT (mg/dL)
- Results of 3hr 100 g OGTT (mg/dL)
- A1C at time of enrollment
- Other comorbidities including but not limited to: hypertension, autoimmune disease, thyroid dysfunction, polycystic ovarian syndrome, cardiac disease, pulmonary disorders, thromboembolic disorders

Vulnerable populations:

- We will not involve vulnerable populations such as those < 18 years old, prisoners, or mentally impaired in this study.

Study design

- Hypothesis:
 - The increased data and feedback provided by real-time CGM will improve glycemic control in gestational diabetic patients over routine SMBG.
- Primary Outcome:
 - Mean blood glucose (mg/dL) in the real-time CGM group compared to SMBG group during the 4th week of study from data collected on the 6 day of CGM use during that week.
- Covariates
- Glycemic outcomes:
 - Between Groups -Failed dietary therapy (started on medication), time spent in normoglycemia week 1 vs. week 4 (min/day), time spent in hyperglycemia week 1 vs. week 4 (min/day), time spent in hypoglycemia week 1 vs. week 4 (min/day)
 - Within Groups - Time spent in normoglycemia week 1 vs. week 4 (min/day), time spent in hyperglycemia week 1 vs. week 4 (min/day), time spent in hypoglycemia week 1 vs. week 4 (min/day)
- Maternal outcomes :

- BMI at time of delivery (kg/m^2)
- Gestational hypertension (defined as SBP ≥ 140 mm Hg or DBP ≥ 90 mmHg, on 2 occasions at least 4 hrs apart)
- Preeclampsia (defined as gestational hypertension plus either new-onset proteinuria (≥ 300 mg/24 2hrs, protein:creatinine ≥ 0.3 mg/dL), thrombocytopenia (platelet count $< 100,000/\mu\text{L}$), elevated AST or ALT ($> 2x$ upper limit of normal), renal insufficiency (serum creatinine > 1.1 mg/dL or an unexplained doubling of creatinine), pulmonary edema, or cerebral or visual symptoms)
- HbA1C values week 1 compared to week 4 (%)

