- There is a risk associated with allowing your data to be saved is the release of personal information from your study record. Research team members will strive to protect patient records such as name, address, social security number, phone number and will notify patient if information is breached.

Statistical Analysis Plan

- Sample Size Calculations:
 - Estimated mean blood glucose of a pregnant women with GDM using CGM: 102.6 mg/dL +/- SD 9 mg/dL²⁴
 - Randomized trial, 1:1 allocation, continuous variable outcome
 - Alpha = 0.05
 - Beta = 0.80
 - 10 patients/arm to detect a 20% decrease in mean blood glucose
 - Goal: 20 patients/arm with interim analysis after 10 patients/arm have completed the trial
- Other analysis will be with the guidance and aide of EVMS CHAD:
 - All data will be analyzed with intention to treat. Normality of data will be tested for all continuous variables using the Kolmogorov–Smirnov test. Normally distributed parameters will be presented as mean±SD, and non-normally distributed values are presented as median (range). Categorical data will be reported as frequency and percentage. Parametric (the Student's t-test) or nonparametric (the Mann–Whitney U-test) comparisons will be used based on the distribution of variables. The pre/post change in blood glucose between the two arms will be compared using regression models, when treatment group will be treated as a qualitative independent variable. To assess the significant difference between the two arms adjusting for covariates, ANCOVA model will be used.. A p < 0.05 will be accepted as statistically significant. SAS 9.4 (SAS Institute Inc, Cary, NC) will be used for statistical analysis.

REFERENCES:

1. Bulletins--Obstetrics CoP. Practice Bulletin No. 137: Gestational diabetes mellitus. *Obstet Gynecol*. 2013;122(2 Pt 1):406-416.
2. Moyer VA, Force USPST. Screening for gestational diabetes mellitus: U.S. Preventive Services Task Force recommendation statement. *Ann Intern Med*. 2014;160(6):414-420.
4. Wier LM WE, Burgess J, Elixhauser A. Hospitalizations related to diabetes in pregnancy. In.

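### A normality test on the outcome data decides whether the primary outcome, week-4 mean glucose, is analysed as a difference in means or by ranks and medians

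*Protocol*

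**What the plan says.** Protocol, Study design, Primary Outcome: "Mean blood glucose (mg/dL) in the real-time CGM group compared to SMBG group during the 4th week of study".

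Protocol, Statistical Analysis Plan, Sample Size Calculations: the expected mean is 102.6 mg/dL with SD 9, and the plan sizes the trial as "10 patients/arm to detect a 20% decrease in mean blood glucose". It then sets the size and the looks: "Goal: 20 patients/arm with interim analysis after 10 patients/arm have completed the trial".

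Same section, under other analyses: "Normality of data will be tested for all continuous variables" by Kolmogorov–Smirnov. Variables judged normal are shown as mean±SD, while "non-normally distributed values are presented as median (range"). Student's t-test or Mann–Whitney "comparisons will be used based on the distribution of variables".

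Two further analyses follow: "The pre/post change in blood glucose between the two arms will be compared using regression models", and "To assess the significant difference between the two arms adjusting for covariates, ANCOVA model will be used". Neither is called primary, and neither is said to replace the choice between t-test and Mann–Whitney.

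**The concern.** The plan states a rule, and by its wording the rule covers every continuous variable, so it covers the primary outcome. The plan asks about a difference in means and sizes the trial on one. Mann–Whitney compares how values in the two arms rank against each other, and a median with range gives no estimate of a mean difference. Which question the trial answers would therefore be settled by a test on the outcome data themselves.

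That test has 10 or 20 observations per arm to work with, so both its misses and its false alarms matter. A switch could come from chance alone, and the interim and final analyses of the same outcome could end up on different tests and different summaries.

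**Working it through.** **Inputs.** From the Protocol: mean 102.6 mg/dL, SD 9, a 20% decrease, alpha 0.05, 1:1 allocation, 20 per arm with a look at 10 per arm. Assumed because not stated: two-sided testing, pretest level 0.05, pretest run in each arm, a switch if either arm is flagged, and critical values corrected for an estimated mean and SD. The Protocol gives no distribution for glucose, so every non-normal shape below is an assumption.

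**1. The plan's own figure.** The difference is 0.20 × 102.6 = 20.52 mg/dL. The usual two-mean formula gives n = 2 × (1.960 + 0.842)² × 9² / 20.52² ≈ 3.02, so 4 per arm (5 by the noncentral t). The stated 10 is not reproduced. That is a separate matter. What counts here is that the calculation is for a difference in means. At 20 per arm the detectable difference at 80% power is 9 × √(2/20) × 2.802 ≈ 8.0 mg/dL, or 7.8% of 102.6.

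**2. Switching by chance.** With normal data, each arm is flagged with probability 0.05. P(at least one arm flagged) = 1 − 0.95² = 9.75%. Simulation at 20 per arm gives 9.7%. A lognormal with the Protocol's own coefficient of variation (9/102.6) gives about 11%.

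**3. Catching real skewness.** Share of samples flagged:

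| Shape | 10 in one arm | 20 in one arm | 40 pooled | 20 in one arm, uncorrected |
|---|---|---|---|---|
| Skewness 1 | 11% | 18% | 33% | 0.2% |
| Skewness about 1.75 (lognormal) | 18% | 34% | 61% | 1.6% |
| Exponential | 30% | 58% | 90% | 4.0% |

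The first three columns use corrected critical values (0.192 at n = 20). The last uses the uncorrected value (0.294). The same sentence in the plan can therefore mean a test that almost never switches or one that switches often.

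**4. Interim against final.** With normal data the looks at 10 and 20 per arm fall on different tests in roughly 13 to 14% of trials. When only some control women run high (the third row of the table in step 6), the figure is about 31%.

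**5. Type I error at 20 per arm.** From normal to exponential data, the two-stage rule gives 5.2 to 5.4% and a fixed t-test 4.6 to 5.0%. The pretest is therefore not needed to protect the error rate. With no true difference, t-test and Mann–Whitney disagree on p < 0.05 in 2.0 to 3.6% of trials.

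**6. Power at 20 per arm.**

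| Assumed shape | Fixed t | Two-stage rule |
|---|---|---|
| Normal, SD 9, difference 6 | 53.6% | 53.5% |
| Normal, SD 9, difference 8 | 78% | 78% |
| 4 of 20 control women 30 mg/dL higher, none in the CGM arm | 25% | 20 to 21% |
| 3 of 20 women high in both arms, shift 8 | 36% | 47% |
| Gamma, skewness 1.75, both arms, shift 8 | 78 to 79% | 88 to 89% |

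In the third row the mean difference is 30 × 4/20 = 6 mg/dL. The control variance is 9² + 30² × 0.2 × 0.8 = 81 + 144 = 225, so the control SD is 15, not 9.

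**The case against.** Three arguments for leaving the plan alone deserve weight.

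First, under the Protocol's own figures with normal data the rule costs almost nothing: at most a few tenths of a point of power, and type I error near 5%. This stands. A reader might infer that the pretest inflates false positives or generally loses power, and the calculations support neither. After a passed pretest the t-test's conditional error reaches 7.8% for exponential data, but the rule as a whole stays at 5.4%. The power loss appears when high values sit only in the control arm, and it reverses when both arms are skewed. Nothing in the Protocol says which shape to expect.

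Second, a reader might infer that on the Mann–Whitney branch the trial could not report a mean difference at all. That goes too far. Regression on change and ANCOVA are listed with no normality condition, and both yield mean differences. But neither is named primary, so the distribution-dependent choice remains the stated rule for a direct comparison of week-4 values. It is also possible to read the primary outcome's mean as each woman's own average over her CGM readings, with the contrast between arms left open. The sample-size line, which refers to a decrease in mean glucose, points to a difference in means.

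Third, a separate SAP might settle the primary model. It might, but the Protocol does not leave the matter open. It states a rule, and that rule is what is at issue.

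The mechanics are also partly assumed. With uncorrected critical values the rule would nearly always give the t-test, so the 10% figure holds only for corrected testing in each arm.

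**Conclusion.** The point holds as a minor one. As written, a Kolmogorov–Smirnov result on the outcome data can move the primary comparison from a difference in means to a rank test with medians, which is not the quantity that the trial names and is sized on. With corrected testing in each arm, that happens by chance in about 10% of trials with normal data at 20 per arm. The interim and final looks can disagree on which test applies.

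The harm is that the estimand depends on the data. It is not loss of error control, and it is not a general loss of power: the effect on power is negligible for normal data, about 4 points lost if only control women run high, and about 10 points gained if both arms are skewed. These figures rest on the assumed shapes and on pretest details that the Protocol does not give.

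**What to change.** Remove the normality pretest as the decision rule for the primary outcome. Name one mean-based analysis of week-4 glucose in advance: either the linear/ANCOVA model already listed, with its covariates fixed, or a Welch t-test. Choose one of these, use it at both looks, and report the mean difference with its 95% CI whatever the distribution looks like. Keep Mann–Whitney as a sensitivity analysis. For secondary outcomes expected to be skewed, such as time in hypoglycemia or length of NICU stay, assign the rank test in advance.

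The cost is one paragraph of wording, with no extra patients or data. Where only control women run high, a Welch test has about 24% power against 25% for Student's t, so little is given up there. The real downside is some lost power for a pure shift if glucose proves strongly skewed in both arms. The Mann–Whitney sensitivity analysis would show that.

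### The general test rule names no paired method, so a non-normal within-group week 1 vs. week 4 outcome would go to the Mann–Whitney U-test, which ignores that the same women are measured twice

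*Protocol*

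**What the plan says.** Under Study design, the glycemic outcomes come in two sets, one between groups and one within groups. The within-group set opens with "Within Groups - Time spent in normoglycemia week 1 vs. week 4 (min/day") and continues with time in hyperglycemia and in hypoglycemia over the same two weeks. Each woman supplies both values.

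The maternal outcomes include "HbA1C values week 1 compared to week 4". This item is not labelled within-group or between-group.

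The section headed Statistical Analysis Plan first has normality of all continuous variables tested, then states the rule: "Parametric (the Student's t-test) or nonparametric (the Mann–Whitney U-test) comparisons will be used based on the distribution of variables". Two further methods follow, both for between-arm differences: "The pre/post change in blood glucose between the two arms will be compared using regression models" and "To assess the significant difference between the two arms adjusting for covariates, ANCOVA model will be used". The protocol names no paired t-test, Wilcoxon signed-rank test, repeated-measures analysis or mixed model.

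The primary outcome is a comparison between arms: "Mean blood glucose (mg/dL) in the real-time CGM group compared to SMBG group during the 4th week of study".

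**The concern.** A within-group week 1 vs. week 4 outcome asks whether each woman changed. Its precision depends on how strongly her two values are correlated. A two-sample test takes the two sets of values as coming from different women, so its variance and reference distribution leave that correlation out.

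Mann–Whitney has no paired form, so the nonparametric branch of the rule does not fit these outcomes. The parametric branch is ambiguous: Student's t-test can be paired, but naming it beside Mann–Whitney suggests the two-sample form. Minutes per day in hypoglycemia may well be skewed (an assumption, since the protocol gives no distribution). The rule would then send that outcome to Mann–Whitney.

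At stake is a moderate within-woman change, possibly a rise in time in hypoglycemia, that is reported as not significant although a paired test on the same data would more often detect it.

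**Working it through.** **The plan's own figure.** The only sample-size statement is "10 patients/arm to detect a 20% decrease in mean blood glucose", from "102.6 mg/dL +/- SD 9 mg/dL". It concerns mean glucose between arms.
- Difference: 0.20 × 102.6 = 20.52 mg/dL; 20.52 / 9 = 2.28 SD.
- Normal approximation, two-sided alpha 0.05, the stated beta of 0.80 read as power: n = 2 × (1.960 + 0.842)² / 2.28² = 3.02, so 4 per arm. The t distribution gives 4.23, so 5.

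The stated 10 is therefore not the minimum that these inputs imply. This has no bearing on the present point. The protocol gives no SD, correlation or power for the within-group outcomes.

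**Inputs for the check**
- Pairs per arm: 20 (the sample-size goal in the Statistical Analysis Plan section).
- Alpha: 0.05, taken as two-sided.
- Assumed: normal data, equal SD in both weeks, r from 0 to 0.8, true change of 0.5 SD (also 1 SD).

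**Standard errors of the mean change, in SD units**
- Two-sample: √(2/n) = √(2/20) = 0.316.
- Paired: √(2(1 − r)/n). At r = 0.5 this is √(1/20) = 0.224.
- Ratio: 1/√(1 − r).

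**Simulated rejection rates.** Both kinds of test were applied to the same paired data, with 100,000 runs for the t-tests and 20,000 for the rank tests. Type I error is the rejection rate with no true change; power is for a change of 0.5 SD.

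| r | SE ratio | Type I error, two-sample t | Power, two-sample t vs. paired t | Power, Mann–Whitney vs. signed-rank |
|---|---|---|---|---|
| 0 | 1.00 | 5.0% | 34% vs. 32% | 32% vs. 30% |
| 0.3 | 1.20 | 2.1% | 31% vs. 43% | 30% vs. 42% |
| 0.5 | 1.41 | 0.7% | 29% vs. 56% | 27% vs. 54% |
| 0.7 | 1.83 | 0.1% | 25% vs. 78% | 24% vs. 76% |
| 0.8 | 2.24 | 0.01% | 22% vs. 92% | 22% vs. 90% |

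Mann–Whitney has a type I error of 0.9% at r = 0.5, close to the two-sample t-test.

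**Larger change.** For a change of 1 SD at r = 0.5, two-sample vs. paired t-test power is 94% vs. 99%.

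**Reading the results.** At r = 0 the paired test is slightly worse, because it has 19 degrees of freedom and not 38. From r = 0.3 upward it is better at 0.5 SD, by 12 points at r = 0.3 and 70 points at r = 0.8.

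**The case against.** **The rule may not be meant for these outcomes.** It is generic, and the next two methods concern differences between arms. One can read the two tests as between-arm tests and the within-arm method as left to a separate SAP or to the statistical support that the section mentions. This lowers certainty but does not settle the matter. The section is itself headed Statistical Analysis Plan and fixes the tests, the normality rule that chooses between them, the significance threshold and the software. A reader who applies its only general rule to a listed non-normal outcome arrives at Mann–Whitney.

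**Stronger readings that the protocol does not support**
- *Every named test is for independent samples.* This is certain only for Mann–Whitney. Student's t-test has a paired form, which the text does not exclude.
- *The null hypothesis is wrong.* For the t-test, equal means is still the hypothesis. The variance and reference distribution are what go wrong, and with positive correlation there are fewer false positives, not more.
- *Confidence intervals or error bars would be wrong.* None are planned for these outcomes. The planned summaries, mean with SD or median with range, do not depend on pairing.
- *HbA1C is affected too.* It is listed under maternal outcomes, and the between-group items use similar week 1 and week 4 wording. It is affected only if it is analysed within arm.
- *Power is lost in any case.* The loss needs a positive correlation, which is plausible for one woman's glucose a few weeks apart but is not given. It also needs a moderate change. At r = 0.3 and 0.5 SD, the paired t-test itself has only 43% power.

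**Importance.** These are secondary contrasts within arms, not randomized comparisons. The effect of real-time CGM is judged between arms.

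**Conclusion.** The point holds in a limited form. The protocol lists three within-group outcomes on the same women, and its one general test rule has a nonparametric branch that cannot handle them and a parametric branch that does not say whether it is paired. No other named method fills the gap.

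The size depends on r and on the change, both assumed. For 20 women and 0.5 SD, a two-sample t-test costs nothing at r = 0, 12 points of power at r = 0.3, 27 at r = 0.5 (29% vs. 56%) and 53 at r = 0.7. The rank tests behave alike. The cost is minor for changes near 1 SD.

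A reader might infer that the trial's main conclusion is at risk. It is not: the primary outcome and the other between-arm comparisons are unaffected. This is a correction to make before analysis, confined to secondary outcomes.

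**What to change.** In the Statistical Analysis Plan section, limit the two-sample t-test and the Mann–Whitney U-test to between-arm comparisons, and add a sentence such as:

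> *Within-arm comparisons of week 1 with week 4 (time in normoglycemia, hyperglycemia and hypoglycemia) will use each woman's paired difference, with the paired t-test or the Wilcoxon signed-rank test chosen on the distribution of the differences.*

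State whether HbA1C is compared within or between arms, and add it to this sentence only if within.

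The cost is one or two sentences. The weekly CGM data are already collected on each woman, and both tests are standard. The small downside is that a woman lacking one of the two weeks drops out of the paired comparison.
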